- 3. To perform immune monitoring in the circulation and in the tumor microenvironment while on therapy with pembrolizumab specifically, the frequency of circulating T cell populations, including NY-ESO-1 specific cytotoxic T cells, as well as T cell infiltration in available pre- and post- therapy tumor tissues will be assessed.

Trial Design

This is an open-label phase II study of pembrolizumab given at 200 mg IV every 3 weeks in patients with locally advanced or metastatic bone and soft tissue sarcomas.

Maximum Total Number of Patients

Initial enrollment was 86 patients: patients with soft tissue sarcomas and patients with bone sarcomas

In an expansion study, there will be an additional 60 patients enrolled to the soft tissue cohort: 30 patients with undifferentiated pleomorphic sarcoma and 30 patients with dedifferentiated or other high grade liposarcoma

Target Population

Patients with advanced refractory soft tissue or bone sarcomas

Efficacy Evaluations

Tumor measurements by CT/MRI imaging will be performed initially at 8 weeks and every 12 weeks subsequently - RECIST 1.1 will be the primary outcome measure and immune-related Response Criteria (ir-RC) will be a secondary outcome.

Duration of Participation

Each patient will participate in the trial from the time of Informed Consent Form (ICF) is signed through final protocol-specified contact. After a screening phase for eligibility, patients will receive pembrolizumab every 3 weeks. Treatment for patients that achieve stable disease (SD), a partial response (PR), or a complete response (CR) can continue for a maximum of 2 years total duration of treatment. At the discretion of the investigator, patients who have progressive disease (PD) but continue to achieve clinical benefit, may also continue on therapy for a maximum of 35 cyclestotal duration of treatment.

Safety Evaluations/ Concerns

Safety evaluations will be done according to CTCAE version 4.0 with special emphasis on immune-related adverse events (ir-AEs).

Correlative Studies

Blood for research studies will be collected prior to first study drug administration, at week 8, week 20 and week 32 and flow cytometry analyses will be performed to determine the presence of PD-1 expressing T cells, as well as the proportion of circulating Treg cells and MDSCs.

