2.16 Rationale for the Trial and Selected Patient Population

This study is therefore a Phase II clinical trial to determine the preliminary clinical

efficacy of the anti-PD1 antibody pembrolizumab in patients with advanced sarcomas. Given the heterogeneity of advanced sarcomas, the study will have two separate arms that each encompasses sarcoma subtypes with similar anatomic primary sites and patterns of progression.

In the original 86 patient group, 80 patients were evaluable for objective response rate by RECIST 1.1. Among 40 evaluable patients in the STS cohort, there were 7 partial responses with an ORR of 18%. Four partial responses were seen among 10 patients with undifferentiated pleomorphic sarcoma for an ORR of 40%. Two additional PRs were observed in the dedifferentiated/high grade liposarcoma cohort (2 out of 10) for an ORR of 20%. There was an additional PR seen in the synovial sarcoma cohort. Among 40 evaluable patients in the bone sarcoma cohort, there were 2 partial responses with an ORR of 5%. 1 PR was seen each in the dedifferentiated/high grade chondrosarcoma and osteosarcoma cohorts.

Given the observed PRs in the UPS and dedifferentiated/high grade liposarcoma cohorts, we will enroll patients to expansion of both cohorts to include an additional 30 patients each (UPS and LPS) to further explore and confirm the activity of pembrolizumab.

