13. STATISTICAL CONSIDERATIONS

13.1 Study Design/Endpoints

A patient will be classified as a treatment success if he/she achieves a response of PR or better. On each arm of the study, we will test the hypothesis that pembrolizumab has clinical activity in patients with advanced sarcoma. An objective response rate of 25% will be considered clinically meaningful and a response rate less than 10% will be considered lack of efficacy. In a single stage design, we will accrue 40 patients in each arm. The treatment will be considered a success if 8 or more of 40 enrolled patients have a PR or better by RECIST 1.1. This design has a one-sided type I error of 4.2% and a power of 82% to detect a difference between 10 and 25%.

In the study expansion, the response rates for undifferentiated pleomorphic sarcoma cohort and the poorly differentiated/dedifferentiated liposarcoma cohort will be analyzed separately. In each subtype cohort, we will analyze a total of 40 evaluable patients (10 from part 1 of the study and 30 from the expansion cohort). An objective response rate of 25% will be considered clinically meaningful and a response rate less than 10% will be considered lack of efficacy. The treatment will be considered a success if 8 or more of 40 enrolled patients have a PR or better by RECIST 1.1. This design has a one-sided type I error of 4.2% and a power of 82% to detect a difference between 10 and 25%.

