13.2 Sample Size/Accrual Rate

Initial enrollment was 86 patients: with soft tissue sarcomas and with bone sarcomas

In the expansion study, there will be an additional 60 patients with soft tissue sarcoma enrolled: 30 patients with undifferentiated pleomorphic sarcoma and 30 patients with poorly differentiated/dedifferentiated liposarcoma.

At least 20 patients in each of the undifferentiated pleomorphic sarcoma and poorly differentiated/dedifferentiated cohorts will have mandated biopsies for correlative analysis. The remaining 10 patients in each of the cohorts will not be required to obtain

baseline and 8-week tumor biopsies, although archival tissue will be required for PD-L1 testing.

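### The 82% power for each expansion cohort holds only if all 30 enrolled patients are evaluable; at the pooled part 1 loss rate it would be about 76–77%

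*Combined protocol and SAP*

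**What the plan says.** Section 13.1 defines the analysis set for each expansion cohort (undifferentiated pleomorphic sarcoma, UPS, and poorly differentiated/dedifferentiated liposarcoma, LPS): "we will analyze a total of 40 evaluable patients (10 from part 1 of the study and 30 from the expansion cohort"). The same paragraph gives the hypotheses ("An objective response rate of 25% will be considered clinically meaningful"; "a response rate less than 10% will be considered lack of efficacy") and then the decision rule: "The treatment will be considered a success if 8 or more of 40 enrolled patients have a PR or better by RECIST 1.1". The operating characteristics follow: "This design has a one-sided type I error of 4.2% and a power of 82% to detect a difference between 10 and 25" per cent.

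Section 13.2 sets the recruitment: "In the expansion study, there will be an additional 60 patients with soft tissue sarcoma enrolled: 30 patients with undifferentiated pleomorphic sarcoma", with the same number for liposarcoma. The synopsis repeats the total, under a heading that calls it a maximum: "In an expansion study, there will be an additional 60 patients enrolled to the soft tissue cohort".

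Section 11.1.1 counts a patient as evaluable for response only with measurable disease at baseline, at least one cycle of therapy and a re-evaluation; objective progression before the end of cycle 1 also counts. Section 2.16 reports what this gave in part 1: "In the original 86 patient group, 80 patients were evaluable for objective response rate by RECIST 1.1", with 40 evaluable in each arm.

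**The concern.** The analysis set needs 30 evaluable patients from the expansion, and recruitment supplies 30 enrolled patients. Nothing in the plan covers the gap if some of them cannot be evaluated: there is no inflation of the number, no replacement rule, and no statement of what happens to the threshold of 8 when fewer than 40 are evaluable. The correlative analysis in Section 13.3 does allow for attrition (up to 20% between paired biopsies); the primary endpoint does not.

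Two things are at stake. The chance of missing an active treatment in either cohort is larger than the plan implies. And with fewer than 40 evaluable patients the plan does not say whether 8 responses are still required, so the threshold could be questioned after the data are seen.

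**Working it through.** **Inputs.** Null rate 10%, target rate 25%, at least 8 responses, 40 evaluable = 10 + 30 (Section 13.1). Enrolment of 30 per cohort (Section 13.2 and synopsis). Part 1: 80 evaluable of 86 (Section 2.16). The 10 part 1 patients per subtype are already among the evaluable, so only the 30 new patients are at risk of loss.

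**1. The plan's own figure.** For N evaluable patients, error = P(X ≥ 8) with X ~ Bin(N, 0.10), and power = P(X ≥ 8) with X ~ Bin(N, 0.25). At N = 40 these are 4.19% and 81.8%. The stated 4.2% and 82% reproduce.

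**2. Expected number evaluable.** Loss in part 1 = 6/86 = 7.0%. Expected evaluable in the expansion = 30 × 80/86 = 27.9, so N = 10 + 27.9 = 37.9, about 38. If patients are lost independently at this rate, the chance that all 30 are evaluable is (80/86)^30 = 11.4%.

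**3. The same rule at smaller N.**

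| N evaluable | Error (10%) | Power (25%) |
|---|---|---|
| 40 | 4.2% | 81.8% |
| 39 | 3.7% | 79.4% |
| 38 | 3.2% | 76.9% |
| 37 | 2.7% | 74.1% |
| 36 | 2.4% | 71.0% |

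Averaging over K ~ Bin(30, 80/86) with N = 10 + K gives error 3.2% and power 76.4%. The false-negative risk moves from 18% to about 24%.

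**4. Range from the unknown arm split.** The six losses are not divided between the arms. If none were in the soft tissue arm, N = 40 and power is 82%. If all six were, that arm enrolled 46 to get 40 evaluable, a loss of 6/46 = 13.0%; then 30 × 40/46 = 26.1, N is about 36 and power about 71%.

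**5. If the threshold moved.** Requiring 7 of 38 would give error 8.0% and power 87.2%. The plan does not propose this; the figure shows why the threshold should be fixed in advance.

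**6. What these figures leave out.** They treat all 40 outcomes as unknown. Section 2.16 already reports 4 of 10 responses in UPS and 2 of 10 in LPS, so 4 and 6 more are needed. Given those results:

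| New evaluable | UPS error / power | LPS error / power |
|---|---|---|
| 30 | 35% / 96% | 7.3% / 80% |
| 28 | 31% / 94% | 5.5% / 74% |

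Neither the printed figures nor those in step 3 describe the two cohorts from the point at which the expansion was opened.

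**The case against.** **The rule is worded on enrolled patients.** The success rule in Section 13.1 says 40 enrolled, and the synopsis (Brief Statistical Design) gives a total of 40 patients per subtype without the word evaluable. If the denominator is enrolled patients and the 25% rate refers to all of them, 10 + 30 = 40 and 82% stands. This is right as far as it goes. But the same paragraph of 13.1 sets the analysis on evaluable patients. If unevaluable patients instead count as non-responders among 40 enrolled while 25% is the rate in evaluable patients, the number of responses has the same distribution as in the averaged calculation and power is again 76.4%. The plan does not say which population the rates describe.

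**The sponsor may over-enrol, as before.** A reader might infer that recruitment is firmly capped at 30 and that 38 evaluable patients is the settled outcome. The documents do not support that. The word maximum is only a synopsis heading, Section 13.2 states no cap, and part 1 planned 40 per arm (Section 2.17: up to 80) yet enrolled 86 and ended with exactly 40 evaluable in each arm. That pattern is consistent with enrolling until the target was met. No such rule is written for the expansion, however, so the text as it stands gives no route to 40 evaluable if any patient is lost.

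**The loss rate is borrowed.** The 7% pools both arms, including bone sarcoma. This stands, and is why a range is needed.

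**Known results matter more for UPS.** Conditional on 4 of 10 responses, power in UPS exceeds 82% with or without the loss. This also stands: the shortfall concerns the unconditional design statement, and a bare restatement of 3% error and 76% power would mislead in its turn.

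**Conclusion.** The printed 4.2% and 82% are computed correctly for 40 evaluable patients, but the written enrolment plan reaches that number only if no expansion patient is unevaluable. At the pooled part 1 loss, about 38 would be evaluable, with error of about 3.2% and power of about 76–77%: a loss of about 5 points, with a plausible range of 71% to 82%. This rests on three assumptions: the 10% and 25% rates apply to evaluable patients, the part 1 loss carries over to these cohorts, and nobody is replaced.

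A reader might also infer that the false-positive rate is inflated. It is not inflated by the loss: while the threshold stays at 8, the unconditional error falls. The defect is a missing attrition allowance together with two conflicting denominators, not a miscalculation.

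**What to change.** In Section 13.1 and the synopsis:

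1. Use one denominator, either evaluable or enrolled, in both the analysis set and the success rule, and say that the 10% and 25% rates refer to that population.
2. If it is evaluable patients, restate the operating characteristics. For example: at the part 1 rate of unevaluable patients (6 of 86, both arms pooled) about 38 evaluable patients per cohort are expected; requiring at least 8 responses then has one-sided type I error of about 3.2% and power of about 76–77%, with power between 71% and 82% for 36 to 40 evaluable.
3. State that the threshold remains 8 responses when fewer than 40 patients are evaluable.
4. Label these as unconditional design figures that do not account for the part 1 responses (UPS 4/10, LPS 2/10) that led to the expansion.

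This changes wording only and adds no patients. The cost is a less favourable stated power. If the sponsor prefers to keep 82%, the alternative is a written replacement rule or enrolment of about 33 per cohort (30 ÷ (80/86) = 32.25, rounded up), which costs about three more patients in each.

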13.2 Sample Size/Accrual Rate

Initial enrollment was 86 patients: with soft tissue sarcomas and with bone sarcomas

In the expansion study, there will be an additional 60 patients with soft tissue sarcoma enrolled: 30 patients with undifferentiated pleomorphic sarcoma and 30 patients with poorly differentiated/dedifferentiated liposarcoma.

At least 20 patients in each of the undifferentiated pleomorphic sarcoma and poorly differentiated/dedifferentiated cohorts will have mandated biopsies for correlative analysis. The remaining 10 patients in each of the cohorts will not be required to obtain

baseline and 8-week tumor biopsies, although archival tissue will be required for PD-L1 testing.

13.3 Analysis of Secondary Endpoints

This design will also allow 87% power to detect an improvement in the 3-months PFS rate from 20% to 40% with a one-sided type I error of 4%.

Progression-free survival will be estimated by the product-limit method. PDL1 expression levels and baseline circulating T cell counts will be related to response via logistic regression, and to PFS via Cox regression. Changes in T cell counts will be related to outcome using appropriate landmarks. Several secondary objectives are clinical and include PFS, OS, ir-RC, and safety all of which will be analyzed taking into account the primary endpoint. All other correlative secondary objectives are exploratory as those data have not been previously reported in sarcoma and therefore will serve as hypothesis generating.

Mandatory pre/post biopsies will be performed for at least 20 patients enrolled in each of the expansion subtype cohorts. Because clear biomarkers for response to pembrolizumab remain to be determined and may not be histology specific, all samples will be evaluated as a single cohort for correlative assessments. PD1 expression on fresh biopsy tissue at both time points will be assessed. Cases will dichotomized into low/high expressers at baseline, and low/high expression changers from pre to post-treatment. Assuming an objective response rate of 10% in tumors with low expression at baseline, this will allow 90% power to detect a difference in objective response of 10% vs 40% using a two-sided 5% level test of proportions. Assuming up to 20% dropout between pre and post biopsies, if 64 patients have both pre and post biopsies, there will be 80% power to detect a difference in objective response of 10% vs 40% between low and high changers, using a two-sided 5% level test of proportions.

Any analyses by individual histologic subtypes will be exploratory only.

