In the initial enrollment and in the first 20 patients enrolled in each of the UPS and LPS cohorts, mandatory biopsies will be obtained during screening prior to initiation of therapy (week 0) and at 8 weeks (\pm 1 week) to coincide with radiologic disease assessment Additional tumor biopsies (optional) at cycle 12 (week 34) and at time of progression may be collected for easily accessible tumors. Surgical excisional biopsies or core biopsies are acceptable.

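### The biopsy-change comparison uses responses that may already exist when the change is measured at week 8, and Section 13.3 states no landmark for it

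*Combined protocol and SAP*

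**What the plan says.** Section 13.3 sorts cases by PD1 expression on fresh biopsies into low and high expressers at baseline, and into "low/high expression changers from pre to post-treatment". For the second split it claims "80% power to detect a difference in objective response of 10% vs 40% between low and high changers". The two rates are to be compared two-sided at the 5% level. The claim is conditional on the number of pairs, "if 64 patients have both pre and post biopsies", and on the loss allowed for, "Assuming up to 20% dropout between pre and post biopsies".

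Three other provisions bear on this comparison:

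- Section 2.17 sets the on-treatment biopsy at 8 weeks, plus or minus one week, "to coincide with radiologic disease assessment". Sections 2.17, 11.1 and 13.4.2 put the first response scan at week 8, with later scans every 12 weeks.
- Section 11.1.4.4 counts best overall response from the start of study treatment, so a response first seen at week 8 is part of the outcome.
- Section 13.3 also says: "Changes in T cell counts will be related to outcome using appropriate landmarks". It has no matching sentence for the biopsy change.

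The same section describes the correlative objectives as exploratory and hypothesis generating.

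**The concern.** When a marker is measured during treatment and the outcome window opens at the start of treatment, the order of events is not fixed. For responses first documented after week 8, the biopsy change comes first. For responses already visible at week 8, the tumour has shrunk by the time the second sample is taken, and the change in expression may be a consequence of that shrinkage. The planned test pools both kinds of response.

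A higher response rate among high changers could then appear although the change predicts nothing. The purpose of the analysis is to suggest biomarkers for later work, so the risk is that a by-product of response is carried forward as a candidate predictor. The plan guards against this for blood markers and is silent for tissue.

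**Working it through.** **1. The plan's own figure.** Inputs from Section 13.3: 10% vs 40%, two-sided 5%, 64 pairs. The split is not stated; 32 per group is assumed. The pooled rate is 0.25.

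- Null SE = √(2 × 0.25 × 0.75 / 32) = 0.1083
- Alternative SE = √((0.10 × 0.90 + 0.40 × 0.60) / 32) = 0.1016
- z = (0.30 − 1.96 × 0.1083) / 0.1016 = 0.865, so power = 80.6%

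This reproduces the stated 80%. With 20% loss, 64 pairs imply 64 / 0.8 = 80 patients at baseline; 40 per group gives 88.8% against the stated 90%. The arithmetic is sound.

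**2. Effect of shared timing when the change predicts nothing.** Assumptions: 64 pairs and a 25% response rate (the mean of 10% and 40%), hence 16 responders and 48 non-responders. A share f of responders already respond at week 8, and each of these is a high changer with probability q. Everyone else is a high changer with probability 0.5. The documents give neither f nor q.

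Expected responders among high changers = 16 × [f q + (1 − f) × 0.5]. Expected non-responders in each group = 24. Rejection rates come from exact enumeration of the two-sided 5% Pearson test.

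| f | q | Responders, high / low | Response rate, high vs low | Test rejects |
|---|---|---|---|---|
| 0 | – | 8.0 / 8.0 | 25% vs 25% | 5% |
| 25% | 70% | 8.8 / 7.2 | 27% vs 23% | 6% |
| 50% | 70% | 9.6 / 6.4 | 29% vs 21% | 10% |
| 50% | 80% | 10.4 / 5.6 | 30% vs 19% | 17% |
| 75% | 90% | 12.8 / 3.2 | 35% vs 12% | 58% |

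For example, in the last row 12.8 / 36.8 = 35% and 3.2 / 27.2 = 12%.

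**3. Missing pairs.** Take 80 patients with 20 responders, and suppose that all 16 lost patients are non-responders. The response rate among pairs rises from 20/80 = 25% to 20/64 = 31%. If the losses would have divided evenly between low and high changers, the contrast stays null: 10/32 vs 10/32. If all 16 would have been high changers, a true 25% vs 25% becomes 10/40 = 25% vs 10/24 = 42%. Loss therefore biases the contrast only if it depends on the marker change as well as on outcome.

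**4. What a landmark costs.** Assume a true 10% vs 40% in 32 per group, drop patients already responding at week 8, and count later responses only. The low group keeps 32 × (1 − 0.1f) patients and the high group 32 × (1 − 0.4f). At f = 50% this is 1.6/30.4 = 5.3% vs 6.4/25.6 = 25%, with power 56%. At f = 25% power is 70%, and at f = 75% it is 35%. This does not model the further removal of patients who have progressed by week 8, whose number is unknown. In a simulation under step 2's null, the landmark returned the rejection rate to about 4% to 5%.

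**5. Sensitivity of the stated power to the split.** Exact power at 64 pairs, low/high: 32/32 gives 83%, 38/26 gives 84%, 45/19 gives 80%, 51/13 gives 70% and 13/51 gives 58%.

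**The case against.** The strongest reply is that the plan does not call the change a predictor. It speaks of a difference in objective response, labels the correlative work hypothesis generating, and rests no success or treatment decision on it. Comparing on-treatment change by response is a legitimate pharmacodynamic association. That stands, and it is why the planned comparison should be kept and relabelled. It does not remove the problem: without a label or a landmark, the result can be read as prediction.

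It is also fair that the size rests on assumed inputs. The milder settings lift the false-positive rate only to 6% or 10%, and nothing in the documents shows that shrinkage alters PD1 expression.

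Two stronger readings are tempting, and neither is supported:

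- A reader might infer that patients who fail before week 8 have no pair and so fall in neither group. The documents do not say this. Sections 2.17 and 5.6 allow treatment past progression, the first scheduled scan is itself at week 8, and a biopsy at progression is optional. Some early failures may lack a pair; how many is unknown.
- A reader might infer that the stated 80% power needs an even split. Step 5 shows that it holds to about 70% low and 30% high.

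**Conclusion.** The point holds as a limit on interpretation. The test of low against high changers mixes responses that precede or coincide with the second biopsy with responses that follow it, and Section 13.3 does not extend its landmark to the biopsy change. With no predictive value, the nominal 5% test would reject in about 6% to 58% of trials, depending on two quantities that the documents do not give; 58% is the unfavourable end of the settings examined, not an estimate. Missing pairs are a secondary matter and distort the contrast only under the extra condition in step 3. The stated power is correct for an even split and is reasonably robust, weakening at splits such as 80/20 in either direction. Because the analysis is exploratory and the primary ORR test is unaffected, this is a cheap improvement and not a flaw in the trial's main conclusion.

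**What to change.** In Section 13.3, extend the landmark wording to the biopsy change, with week 8 as the landmark:

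- Among patients alive with a paired biopsy at week 8, relate the change to OS from week 8.
- Among those who are also progression-free, relate it to PFS from week 8.
- Among those who have neither responded nor progressed, relate it to responses first documented after week 8.

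Keep the planned low/high comparison of all responses, but describe it as a concurrent association and not as evidence of prediction. Report responses already present at week 8 separately. Analyse the change as a continuous variable in the logistic and Cox models that the section already uses for PD-L1 level and baseline T-cell counts, and keep the low/high split for display.

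This is a wording change that needs no new visits or samples. The price is fewer events after the landmark. Under the assumptions of step 4, power for the later-response comparison drops from about 80% to about 70%, 56% or 35% as the share of responses present at week 8 rises from 25% to 50% to 75%. For that reason the landmark analyses should accompany the planned comparison and not replace it.
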